4.3. Type and Number of Subjects

A total of at least 534 subjects (267 analyzable subjects per treatment group) may be enrolled in the study. Enrollment will occur in 3 cohorts separated by interim analyses. The trial will continue to subsequent cohorts only if the prospective criteria for discontinuing the trial are not met at the interim analysis:

- at least thirty subjects will be enrolled in Cohort 1,
- at least an additional 70 subjects will be enrolled in Cohort 2 if the study progresses beyond interim 1.
- and at least an additional 434 subjects will be enrolled in Cohort 3 if the study progresses beyond interim 2.

If a subject prematurely discontinues the study prior to the Day 29 primary endpoint measurement, additional subjects will be randomized to reach the required number of analyzable subjects for a given analysis (please refer to Section 9.3.1 for definition of an analyzable subject). The goal will be to only enroll the minimum number of subjects to reach the target number of analyzable subjects. Although the number of randomized subjects who will not be analyzable is unknown, based on expectations of study withdrawal and data from previous trials with AVA, it is estimated that no more than 620 subjects will be randomized to reach the target of 534 analyzable. The decision to randomize additional subjects will be made without knowledge of the ongoing comparative results; if ongoing comparative results are known to the Sponsor, no additional subjects may be enrolled.

4.4. Design Justification

This is a Phase 4 study to evaluate the immunogenicity of SC-administered AVA when administered alone or concomitantly with a single IV raxibacumab dose, in healthy adult volunteers who have not previously been immunized against the PA of *B. anthracis*. Subjects will receive the first AVA dose immediately after completion of a single 40 mg/kg raxibacumab IV infusion. Although this is an open-label study, measures have been introduced to minimize bias (refer to Section 6.3).

As a passive anti-toxin antibody, raxibacumab is expected to provide protection against PA for up to 28 days post dose [Migone, 2009]. The expected, but currently unapproved, use of AVA in combination with raxibacumab would be in the post-exposure prophylaxis setting. In that setting, raxibacumab would provide the initial toxin neutralizing activity while AVA immunization would generate a durable, toxin neutralizing anti-PA Ab response that maintains protection beyond 28 days, since raxibacumab levels may not be adequate for protection for more than 28 days post-infusion. Relative to this, 93% of subjects administered SC AVA doses at Weeks 0, 2, and 4 had at least a 4-fold increase in TNA titer by Week 4, with higher titers than for intramuscular (IM) doses administered according to the same schedule [Marano, 2008]. Based on these findings, this study will utilize SC-administered AVA rather than IM-administered AVA because the immunogenicity of SC-administered AVA early in the immunization series (at week 4) is of primary interest. Because of a lack of assay specificity for TNA response due to AVA when raxibacumab is present, it is not possible to specifically evaluate a 4 fold increase in the TNA titer due to AVA in this study. However, GSK developed analytical techniques which allow specific determination of anti-PA Ab concentrations in response to AVA vaccination, even in the presence of raxibacumab. Therefore, anti-PA Ab concentration will be assessed as the primary endpoint in this study, instead of >4-fold increase in TNA titers. Relative to this, a high correlation between anti-PA Ab levels and TNA has been reported [Crowe, 2010; Pittman, 2002; Pittman, 2005; Pittman, 2006; Quinn, 2004]. Thus, it is reasonable to expect that measurement of anti-PA Ab is reflective of a functional immune response.

Since an immune response to AVA requires some time to develop, it is anticipated that in the post-exposure prophylaxis setting the initial AVA dose would be in close temporal proximity to the raxibacumab dose. For this study, the first AVA dose will be administered immediately after completion of the raxibacumab IV infusion, so that raxibacumab levels are as high as possible when AVA administration starts. This should maximize the potential for raxibacumab to interfere with AVA immunogenicity. A finding of no effect of raxibacumab on AVA immunogenicity in this study can be extrapolated to other timings between raxibacumab and AVA administration since it represents the worst case scenario for a potential interaction between raxibacumab and AVA.

Based on published results, polyclonal anti-PA antitoxin administered to rabbits in combination with AVA resulted in essentially complete abrogation of the immune response to AVA [Malkevich, 2013]. Thus, it is possible that co-administration of raxibacumab with AVA will essentially eliminate any immunogenic response to AVA. Given that expectation, this study will enroll subjects in 3 cohorts, with two interim

analyses to allow early termination of the study if a large effect of raxibacumab on AVA immunogenicity is confirmed at the interim.

Additional description of the interim analyses, including justification for the timing and how they impact the operating characteristics of the study, can be found in Section 9.3.2.

The study duration of 26 weeks was chosen to allow evaluation of the secondary endpoint of AVA immunogenicity, including TNA titer, after raxibacumab is essentially completely eliminated as an assessment of the durable immune response to AVA. Week 26 is of interest since it represents the nadir response at the time when an AVA dose would be administered to boost response. In addition, that study duration allows collection of safety and tolerability data throughout the period of raxibacumab exposure. This is based on data from healthy volunteer studies indicating that >99% of subjects can be expected to attain raxibacumab wash-out (i.e., less than 5% of the administered dose remaining in the body) by week 24.

4.5. Dose Justification

Raxibacumab will be administered in accordance with approved product label dosing recommendations [[Raxibacumab Package Insert, 2012](#)]. Per the package insert, subjects will be premedicated with diphenhydramine (25-50 mg) up to 1 hour prior to the raxibacumab infusion to reduce the risk of infusion reactions.

AVA will be administered in accordance with the approved product label dosing recommendations [[Anthrax Vaccine Adsorbed Package Insert, 2012](#)]. This study will utilize the SC-administered AVA dosing schedule rather than the IM-administered AVA dosing schedule because the immunogenicity of AVA early in the immunization series (at Week 4) is of primary interest. Findings from [Marano et al., 2008](#) indicate that the SC regimen affords superior geometric mean serum anti-PA Ab concentrations and >4-fold responder percentages at 4 weeks post-vaccination, relative to IM administration given on the same schedule. Hence, the SC regimen could be preferable in a post-exposure prophylaxis setting [[Centers for Disease Control and Prevention, 2010](#)].

4.6. Benefit:Risk Assessment

Summaries of findings from both clinical and non-clinical studies conducted with raxibacumab (GSK3068483) can be found in the IB. Summaries of findings from both clinical and non-clinical studies conducted with AVA can be found in the prescribing information [[Anthrax Vaccine Adsorbed Package Insert, 2012](#)]. The following section outlines the risk assessment and mitigation strategy for this protocol

Clinical parameters will be monitored throughout the study in order to assess the safety and tolerability of AVA when administered alone or concomitantly with raxibacumab. The study design in place will allow in-stream blinded review of the aggregated safety and tolerability data during the study. Refer to protocol Section 7.1 for the timing of all clinical assessments.

Risk Assessment

Potential Risk of Clinical Significance	Summary of Data/Rationale for Risk	Mitigation Strategy
Study Drug		
Infusion Site Reactions (ISRs)	Infusion-related reactions were reported during administration of raxibacumab in clinical trials in healthy volunteers including reports of rash, urticaria, and pruritus.	Subjects will be premedicated with 25-50 mg of diphenhydramine up to 1 hour prior to the raxibacumab infusion, as recommended in the product label. Close monitoring of clinical parameters and adverse events will be conducted to assess effects of infusion site reactions.
Other		
Injection-site reactions	The most common ($\geq 10\%$) local (injection-site) adverse reactions observed in clinical studies with AVA were tenderness, pain, erythema, edema, and arm motion limitation.	Close monitoring of clinical parameters and adverse events will be conducted to assess effects of injection-site reactions.

4.6.1. Benefit Assessment

An individual may benefit from participation in this study due to the following:

- Physical exam and hematology and clinical chemistry assessments conducted as part of the study procedures.
- Participation in this study could contribute valuable information on the immunogenicity of AVA administered alone or concomitantly with raxibacumab.

Since no subject will receive the full AVA immunization series as part of this study, no subject should be considered to have a durable anti-PA Ab response at completion of the study. Hence, the subject should be considered to be at risk if exposed to anthrax.

4.6.2. Overall Benefit:Risk Conclusion

Taking into account the measures taken to minimize risk to subjects participating in this study, the potential risks identified in association with this study are justified by the anticipated benefits that may be afforded to subjects.

5. SELECTION OF STUDY POPULATION AND WITHDRAWAL CRITERIA

Specific information regarding warnings, precautions, contraindications, adverse events, and other pertinent information on the GlaxoSmithKline (GSK) investigational product or other study treatment that may impact subject eligibility is provided in the raxibacumab, diphenhydramine, and AVA package inserts.

Deviations from inclusion and exclusion criteria are not allowed because they can potentially jeopardize the scientific integrity of the study, regulatory acceptability or subject safety. Therefore, adherence to the criteria as specified in the protocol is essential.

5.1. Inclusion Criteria

A subject will be eligible for inclusion in this study only if all of the following criteria apply:

1. Healthy as determined by the Investigator or medically qualified designee based on a medical evaluation including medical history, physical examination and laboratory tests
2. Men and women between 18 to 65 years of age
3. Willing and able to adhere to the procedures stated in the protocol.
4. Female subject is eligible to participate if she is not pregnant (as confirmed by a negative serum or urine human chorionic gonadotrophin (hCG) test), not lactating, and at least one of the following conditions applies:

A. Non-reproductive potential defined as:

- Pre-menopausal females with one of the following:
 - Documented tubal ligation
 - Documented hysteroscopic tubal occlusion procedure with follow-up confirmation of bilateral tubal occlusion
 - Hysterectomy
 - Documented Bilateral Oophorectomy
- Postmenopausal defined as 12 months of spontaneous amenorrhea [in questionable cases a blood sample with simultaneous follicle stimulating hormone (FSH) and estradiol levels consistent with menopause (refer to laboratory reference ranges for confirmatory levels)]. Females on hormone replacement therapy (HRT) and whose menopausal status is in doubt will be required to use one of the highly effective contraception methods if they wish to continue their HRT during the study. Otherwise, they must discontinue HRT to allow confirmation of post-menopausal status prior to study enrollment.

B. Reproductive potential and agrees to follow one of the options listed in [Appendix 3](#) requirements, the GSK Modified List of Highly Effective Methods for Avoiding Pregnancy in Females of Reproductive Potential (FRP), from 30 days prior to the first dose of study medication and until after the last dose of study medication and completion of the follow-up visit at Day 183 (at least five terminal half-lives for raxibacumab).

5.2. Exclusion Criteria

A subject will not be eligible for inclusion in this study if any of the following criteria apply:

1. Concurrently participating in another clinical study, at any time during the study period, in which the subject has been or will be exposed to an investigational or non-investigational study vaccine/product (pharmaceutical product or device).
2. Be a member of the military, a laboratory worker, first responder, health care worker, or otherwise be at higher risk of exposure to anthrax
3. History of regular alcohol consumption within 1 month of the study defined as:
 - An average weekly intake of >14 drinks for males or >7 drinks for females. One drink is equivalent to 12 g of alcohol: 12 ounces (360 ml) of beer, 5 ounces (150 ml) of wine or 1.5 ounces (45 ml) of 80 proof distilled spirits.
4. Female planning to become pregnant or planning to discontinue contraceptive precautions before the Day 183 study visit.

5. Pregnant (confirmed by a serum or urine hCG test) or lactating female.
6. ALT and bilirubin >1.5xULN (isolated bilirubin >1.5xULN is acceptable if bilirubin is fractionated and direct bilirubin <35%).
7. Current or chronic history of liver disease, or known hepatic or biliary abnormalities (with the exception of Gilbert's syndrome or asymptomatic gallstones).
8. Any confirmed or suspected immunosuppressive or immunodeficient condition resulting from disease (e.g., malignancy, human immunodeficiency virus [HIV] infection) or immunosuppressive/cytotoxic therapy (e.g., medications used during cancer chemotherapy, organ transplantation or to treat autoimmune disorders).
9. Presence of hepatitis B surface antigen (HBsAg), positive hepatitis C antibody test results at screening or within 3 months prior to first dose of study treatment.
10. A positive pre-study drug/alcohol screen.
11. A positive test for HIV antibody.
12. History of sensitivity to any of the study medications, or components thereof (especially latex and aluminium) or a history of other known drug allergies that, in the opinion of the Investigator or GSK Medical Monitor, contraindicates their participation. Refer to raxibacumab, diphenhydramine and AVA package inserts for product specific information [[Anthrax Vaccine Adsorbed Package Insert, 2012](#); [Raxibacumab Package Insert, 2012](#); [Diphenhydramine Package Insert](#)].
13. Have previously been vaccinated against PA.
14. Have an anti-PA Ab concentration >2 times the lower limit of quantitation at screening.
15. Administration of immunoglobulins not included in this trial and/or any blood products within the 3 months preceding the first dose of study vaccine or planned administration during the study period.
16. Administration of long-acting immune-modifying drugs (e.g. infliximab) within six months prior to the first vaccine dose or expected administration at any time during the study period.
17. Chronic administration (defined as more than 14 consecutive days) of systemic immunosuppressants or other immune-modifying drugs within six months prior to the first vaccine dose. Inhaled, topical and intra-articular corticosteroids are allowed.
18. Administration or planned administration of a vaccine not foreseen by the study protocol within the period starting 35 days before the first dose of study vaccine(s) and ending 30 days after the last dose of study vaccine. This includes

- any type of vaccine such as (but not limited to) live, inactivated, and subunit vaccines. Influenza vaccines are permitted after Week 8.
19. Subjects must abstain from taking prescription or non-prescription drugs (including vitamins and dietary or herbal supplements), within 7 days (or 14 days if the drug is a potential enzyme inducer) or 5 half-lives (whichever is longer) prior to the first dose of study medication until completion of the follow-up visit, unless in the opinion of the Investigator and sponsor the medication will not interfere with the study. Refer to Section [6.10.1](#) for permitted medications.
 20. Exposure to more than four new chemical entities within 12 months prior to the first dosing day.
 21. Any condition which, in the opinion of the investigator, prevents the subject from participating in the study.

5.3. Screening/Baseline/Run-in Failures

Screen failures are defined as subjects who consent to participate in the clinical trial but are never subsequently randomized. In order to ensure transparent reporting of screen failure subjects, meet the Consolidated Standards of Reporting Trials (CONSORT) publishing requirements, and respond to queries from Regulatory authorities, a minimal set of screen failure information is required including Demography, Screen Failure details, Eligibility Criteria, and any Serious Adverse Events (SAE).

Subjects who initially do not meet eligibility criteria may be re-screened one time if their potential eligibility status has changed. Eligible subjects may then be enrolled in this study.

5.4. Withdrawal/Stopping Criteria

Criteria for study treatment withdrawal may include:

- Sponsor terminates the study
- Subject lost to follow-up
- Subject withdraws consent
- Protocol deviation
- Investigator discretion
- Subject experiences an adverse event(s) that is considered to be related to study drug or study procedures and is severe enough in nature to warrant treatment discontinuation.
- Pregnancy (confirmed by a serum or urine hCG test)

Subjects withdrawn from study treatment will be permitted to continue on the study. Subjects withdrawn from the study due to safety reasons or pregnancy will continue to be followed for safety data until resolution of the safety event and for pregnancy outcomes (please refer to [Appendix 5](#) and Section [7.4.1](#) for additional information).

The following actions must be taken in relation to a subject who fails to attend the clinic for a required study visit:

- The site must attempt to contact the subject and re-schedule the missed visit as soon as possible.
- The site must counsel the subject on the importance of maintaining the assigned visit schedule and ascertain whether or not the subject wishes to and/or should continue in the study.
- In cases where the subject is deemed ‘lost to follow up’, the investigator or designee must make every effort to regain contact with the subject (where possible, 3 telephone calls and if necessary a certified letter to the subject’s last known mailing address or local equivalent methods). These contact attempts should be documented in the subject’s medical record.
- Should the subject continue to be unreachable, only then will he/she be considered to have withdrawn from the study with a primary reason of “Lost to Follow-up”.

A subject may withdraw from study treatment at any time at his/her own request, or may be withdrawn at any time at the discretion of the investigator for safety, behavioural or administrative reasons. If a subject withdraws from the study, he/she may request destruction of any samples taken, and the investigator must document this in the site study records.

The reason(s) for a subject not completing the study will be recorded in the Case Report Form (CRF), and the investigator must document, if applicable, the reason (if specified by the subject) for withdrawal of consent.

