9. STATISTICAL CONSIDERATIONS AND DATA ANALYSES

9.1. Hypotheses

Given concentrations are often approximately log normally distributed, they are customarily analyzed on a logarithmic (log) scale; a difference in arithmetic means on a log scale becomes a ratio of geometric means when the results of analysis are converted back to the original data scale. Thus, each hypothesis is a statement regarding a ratio of geometric mean concentrations of the anti-PA Ab attributable to AVA.

The null and alternative hypotheses are as follows:

$$H_0: \theta = \mu_{AVA} / \mu_{AVA+Raxibacumab} \geq 1.5$$

$$H_A: \theta = \mu_{AVA} / \mu_{AVA+Raxibacumab} < 1.5$$

Where θ is the ratio of the geometric mean concentrations (GMCs); μ_{AVA} and $\mu_{\text{AVA}+\text{Raxibacumab}}$ are the population GMCs of the anti-PA Ab attributable to AVA for the two arms.

The null hypothesis is that the ratio of the GMC of anti-PA Ab attributable to AVA in the AVA arm to the GMC of anti-PA Ab in the AVA+ raxibacumab arm is greater than or equal to 1.5. The alternative hypothesis is that the ratio is less than 1.5.

As described above, the non-inferiority margin for the ratio of the geometric means was selected to be 1.5. This is the same margin selected in [Marano et al. \(2008\)](#) based on guidances from the FDA and ICH (International Conference on Harmonisation of Technical Requirements for Registration of Pharmaceuticals for Human Use) and literature precedent.

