9.2. Sample Size Considerations

9.2.1. Sample Size Assumptions

The sample size calculation is based on the assumption that the individual values will be analyzed after being transformed by \log_{10} resulting in data that is approximately normal. In the transformed data the analysis of the ratio of the means is equivalent to a difference of mean values with a margin of $\log_{10}(1.5) = 0.176$.

The standard deviation of the \log_{10} transformed data is assumed to be 0.75. This is selected based on the fact that the sample size in [Marano et al. \(2008\)](#) was based on a standard deviation of 0.45 based on the data from [\[Pittman, 2002\]](#), but the results from the [Marano et al. \(2008\)](#) study had higher standard deviations suggesting an estimate closer to 0.85.

The sample size is calculated assuming 1:1 randomization and two interim analyses for futility after 30 and 100 analyzable subjects. The boundaries for the futility analysis are based on Rho family error spending function with a rho of 0.5. For the purposes of the sample size calculation, the power will be calculated under the alternative hypothesis setting, where the ratio is 1, or equivalence between the two arms with respect to concentrations of anti-PA antibody. With a type 1 error of 5% one-sided a sample size of 534 subjects will allow for 80% power to make a claim of non-inferiority (margin of 1.5), if the true ratio between the geometric means is 1. In a trial of 534 patients, the largest observed GMC ratio between the AVA and the combination that results in a statistically significant non-inferiority result is an estimated ratio of 1.173. This can alternatively be viewed as a minimum observed anti-PA concentration due to the addition of AVA in the combination of ~85% of the concentration when AVA is administered alone. This is under the assumption that the observed variability in the study population is similar to the study design assumption.

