4.11 Primary Analysis

At the final analysis, the non-inferiority test will be based on the CI for the ratio of anti-PA Ab (attributable to AVA) GMCs between the AVA and the AVA + raxibacumab groups at Week 4. This analysis will be performed in the per-protocol population. If the upper bound of the 90% CI is less than 1.5, non-inferiority will be established.

This analysis will be repeated in a sensitivity analysis which will use the full ITT population with imputation for subjects without Week 4 anti-PA Ab concentration results. Two methods of imputation will be used for subjects without Week 4 anti-PA Ab concentration results:

1. In the AVA + raxibacumab arm, missing data will be imputed with the first quartile from the non-missing data in this arm. In the AVA arm, missing data will be imputed with the third quartile from the non-missing data in this arm.
2. In the AVA + raxibacumab arm, missing data will be imputed with the lower limit of quantitation (LLQ). In the AVA arm, missing data will be imputed with the maximum from the non-missing data.

The GMCs for each treatment group will be summarized with corresponding 95% CI for the Week 4 timepoint as well as Week 8 and Week 26.

The GMC ratio and GMCs within each cohort and corresponding CIs will be calculated by first log transforming all of the data by a log base 10. A t-test will be performed and CIs will be calculated about the mean logs and the difference of the mean logs. The results will be transformed back to the original scale by exponentiation, again using a base 10. The exponentiated differences of the sample mean logs will be the ratio of the sample geometric means of the untransformed results.

Welch's unequal variances *t*-test will be performed to assess the sensitivity of the results to the assumption of equality of variances between the anti-PA Ab concentrations in the two treatment groups.

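### Protocol 5.4 makes follow-up after stopping study treatment optional, which costs the ITT sensitivity analyses Week 4 values; the primary per-protocol analysis is not affected

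*Protocol*

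**What the plan says.** **Stopping and staying.** Protocol 5.4 opens its list with "Criteria for study treatment withdrawal may include". The list includes loss to follow-up, withdrawal of consent and termination by the sponsor, which end study participation, alongside adverse events, pregnancy, protocol deviation and investigator discretion. It then says "Subjects withdrawn from study treatment will be permitted to continue on the study". Continued follow-up is stated as a duty only for subjects withdrawn from the study for safety reasons or pregnancy, and only for safety data and pregnancy outcome.

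**Who is analyzable.** Protocol 5.6 and 9.3.1 require the Day 1 and Day 15 AVA doses, raxibacumab if assigned, and a Week 4 anti-PA result. SAP 4.2.3 adds that the AVA doses must fall within the visit window. The per-protocol set consists of the analyzable subjects and is used for the primary analysis.

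**Making up the number.** Under protocol 4.3, when someone leaves the study before the Day 29 measurement, "additional subjects will be randomized to reach the required number of analyzable subjects for a given analysis". Enrolment aims at 534 analyzable subjects, with an estimated ceiling of 620 randomized.

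**ITT analyses.** Protocol 9.4.1 plans three: one in ITT subjects who have a Week 4 result, and two with filled values. The first fill uses the first quartile in the combination arm and the third quartile in the AVA arm. The second uses the lower limit of quantitation and the maximum. SAP 4.11 carries forward only the filled versions, in the "full ITT population with imputation for subjects without Week 4 anti-PA Ab concentration results". SAP 4.13 does not list the omission as a change.

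**The concern.** The trial is open-label, treatment is revealed on Day -1, and the primary analysis removes subjects after randomization. The ITT analyses are the check on that removal. They can do the job only if the removed subjects' Week 4 values are observed.

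The subject of interest stops treatment before the Day 15 dose but can still be reached. The Day 29 anti-PA draw is already on the schedule for both arms (protocol 7.1, Tables 2 and 3). Because staying on study is merely allowed, and because treatment stops and study exits share one list, a site can reasonably treat the stop as an exit. No sentence makes the Day 29 sample the default after treatment stops. Enrolment restores the per-protocol count, so nothing in the target number brings the lost sample to light.

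Under the SAP the lost value is then replaced by one unfavourable to non-inferiority. With many such values, the filled ITT analyses mostly report the filling rule and say little about whether the exclusions biased the ratio.

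**Working it through.** **Inputs**
- Design: "With a type 1 error of 5% one-sided a sample size of 534 subjects will allow for 80% power", at a true ratio of 1 (protocol 9.2.1).
- Margin: "the non-inferiority margin for the ratio of the geometric means was selected to be 1.5" (protocol 9.1); log10(1.5) = 0.1761.
- SD: for the log10 scale, the SD of the "transformed data is assumed to be 0.75" (protocol 9.2.1).
- Interims: "The sample size is calculated assuming 1:1 randomization and two interim analyses for futility after 30 and 100 analyzable subjects" (protocol 9.2.1). The t boundaries are 1.0274, 0.4437 and -1.645 (protocol 9.3.2).
- Ceiling of 620 randomized for 534 analyzable (protocol 4.3).

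**Step 1: reproduce the plan's own figures.** With 267 per arm, SE = 0.75 × √(2/267) = 0.0649. The largest passing ratio is 10^(0.1761 − 1.645 × 0.0649) = 1.173, as stated. Power without interims is 85.7%. With looks at 15, 50 and 267 per arm and the stated boundaries, a multivariate normal calculation gives 79.99%, against the stated 80%.

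**Step 2: upper bound on non-analyzable subjects.** 620 − 534 = 86, and 86/620 = 13.9%. Split evenly, that is 43 of 310 per arm.

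**Step 3: shift from the quartile fill.** A normal quartile lies 0.6745 SD from the mean, so the filled values in the two arms differ by 2 × 0.6745 × 0.75 = 1.012 on the log10 scale. The ITT difference moves by the missing fraction times 1.012. At 43/310 this is 0.1387 × 1.012 = 0.140, and 10^0.140 = 1.38, although the true ratio is 1.

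**Step 4: chance of meeting 1.5.** The variance within a filled arm is (267/310) × 0.5625 + (267/310)(43/310) × 0.506² = 0.515, so the SD is 0.718 and the computed SE is 0.718 × √(2/310) = 0.0577. The estimate must fall below 0.1761 − 1.647 × 0.0577 = 0.081. Its mean is 0.140 and its sampling error is about 0.0649, so z = (0.081 − 0.140)/0.0649 = −0.91, or about 18%. Two simulations of 4,000 trials each (pooled t, final analysis only, interim stops ignored) gave 18.3% and 18.5%.

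**Step 5: scenarios.** Pass rates are from simulation with a true ratio of 1, equal loss by arm, and recovered values drawn from the same distribution as the rest.

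| No Week 4 value, per arm | Shift (log10) | ITT ratio, quartile fill | Upper 90% limit below 1.5 |
|---|---|---|---|
| 43 of 310 (13.9%) | 0.140 | 1.38 | 18–19% |
| 22 of 310 (about half recovered) | 0.072 | 1.18 | 55% |
| 11 of 310 (about three quarters recovered) | 0.036 | 1.09 | 75% |
| 0 of 310 | 0 | 1.00 | about 90% |
| 14 of 281 (5.0%) | 0.050 | 1.12 | 64% |

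For the last row, the comparator with 267 per arm and nothing missing is about 85%.

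**Step 6: the second fill.** The documents give no numerical lower limit of quantitation. Assuming it lies 1 to 3 SD below the log mean, the ratio is 2.5 to 4.1 at 13.9% missing (0% pass) and 1.39 to 1.65 at 5% missing (0.6% to 12% pass). With the limit 2 SD below the mean, recovering half of the 43 gives 1.82 (0% pass), and recovering three quarters gives 1.35 (17% pass).

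**The case against.** Much of the opposing case stands, and it limits the point.

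- *A reader might infer that everyone who stops treatment is replaced.* The trigger in protocol 4.3 and SAP 2.3 is leaving the study before Day 29. A subject who stops after the Day 15 dose and gives the Week 4 sample stays analyzable under 5.6. Those who stop earlier are made up only because enrolment runs to a count of analyzable subjects.
- *A reader might infer that the protocol has no ITT analysis of observed values.* It has one, in 9.4.1; the SAP drops it. Nor are all the fills extreme: the quartile fill is adverse, and only the limit/maximum fill is extreme. Both work against claiming non-inferiority.
- *A reader might infer that 1.38 is the cost of the permissive wording.* The 86 is a ceiling on non-analyzable subjects. It can include subjects who do have a Week 4 value but missed a dose or were dosed outside the window, and others whom no wording would recover. The documents do not split it.
- *A reader might infer that safety follow-up ends when treatment stops.* Those who stay on study have AE assessments through Day 183.

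The strongest remaining argument is that section 7 makes the schedule mandatory and bars waivers, and that 5.4 requires sites to contact subjects and reschedule missed visits. These duties bind only subjects who remain on study, and the missed-visit steps themselves ask whether the subject wishes to, or should, continue. Remaining is the part that 5.4 leaves optional, so the gap is narrowed but not closed.

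**Conclusion.** The point holds as a cheap improvement of limited reach. It concerns the ITT sensitivity analyses, and the follow-up of subjects who leave after stopping. The per-protocol analysis would exclude a subject without the Day 15 dose even if the Week 4 sample were drawn, so the primary result, the 534 target and the 80% power do not depend on this wording.

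The calculation shows how sensitive the filled ITT analyses are to each uncollected sample: a ratio of 1.38 with an 18–19% pass rate at the 13.9% ceiling, and 1.12 with 64% at 5% missing. It assumes a true ratio of 1, an SD of 0.75 and equal loss by arm. The recovery rows also assume that recovered values resemble the rest, which is a simplification for subjects who missed an AVA dose. The share of missing values that better follow-up would recover is unknown, so no single figure can be put on the gain.

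**What to change.** **Protocol 5.4.** Give separate lists for stopping study treatment and for leaving the study, and record the two separately. Replace the permissive sentence with a default: subjects who stop treatment remain on study and are asked to attend the scheduled Day 29, 57 and 183 visits for anti-PA, TNA and AE assessment (and PK in Group 2), unless they withdraw consent to follow-up. The rules for stopping treatment stay as they are.

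**SAP 4.11.** Restore the protocol 9.4.1 analysis of ITT subjects with available Week 4 results, so that the recovered values are analysed without filling. No further sentence on imputation is needed, because filling is already confined to subjects without a Week 4 result.

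**Cost.** A short amendment to one protocol section and one added analysis in the SAP. The visits and assays are already scheduled. The downside is some extra site effort and stipends for subjects who are off treatment.
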